## 3.0 Background and Significance

### 3.1 The HepQuant SHUNT Test

#### 3.1.1 Overall Experience with the HepQuant SHUNT Test

The HepQuant SHUNT test is blood-based, minimally-invasive, well tolerated by subjects, simple to administer, and test administration does not require expensive equipment or technology. Over 1400 tests have been performed in over 650 persons without adverse event related to the HepQuant SHUNT test.

This experience encompasses healthy controls, and subjects with chronic hepatitis C, non-alcoholic fatty liver disease/non-alcoholic steatohepatitis (NAFLD/NASH), primary sclerosing cholangitis (PSC), hepatocellular carcinoma (HCC), polycystic liver disease, and spans the spectrum from minimal to advanced fibrosis and compensated to decompensated disease [1-21].

#### 3.1.2 Test Administration

The HepQuant SHUNT test is performed after an overnight fast or after at least 5 hours of fasting during the daytime. The HepQuant SHUNT test requires venous access via a standard indwelling intravenous catheter, preferably placed in an antecubital vein. An oral solution of 4D-CA and an injectable solution of 13C-CA mixed with 25% human serum albumin are administered simultaneously. Blood samples are obtained at baseline and at 5±1, 20±2, 45±5, 60±5, and 90±5 minutes after dosing. The serum is separated and sent to the HepQuant laboratory for quantification of concentrations of endogenous cholate, 4D-CA and 13C-CA. Clearances are calculated from AUCs and dose and DSI and SHUNT are derived from the clearances.

#### 3.1.3 Test Analysis and Outputs

The HepQuant SHUNT test outputs are:

- **Systemic HFR.** The intravenous clearance ( $Cl_{iv}$ , mL min) is defined as the dose/AUC for 13C-CA. The Systemic Hepatic Filtration Rate (Systemic

HFR) is defined as the  $Cl_{iv}$  per kg of body weight and is expressed as  $mL\ min^{-1}\ kg^{-1}$ .

- **Portal HFR.** The apparent oral clearance ( $Cl_{oral}$ ,  $mL\ min^{-1}$ ) is defined as the dose/AUC for 4D-cholate. The Portal Hepatic Filtration Rate (Portal HFR) is defined as the  $Cl_{oral}$  per kg of body weight and is also expressed as  $mL\ min^{-1}\ kg^{-1}$ .
- **SHUNT.** SHUNT, the portal-systemic shunt fraction, is calculated as the ratio Systemic HFR/Portal HFR x 100%.
- **DSI.** The calculation for Disease Severity Index is a proprietary formula derived from Systemic HFR and Portal HFR. DSI 0 implies no hepatic impairment and is based on the means (+3 SDs) for Systemic and Portal HFRs of normal weight healthy volunteers. DSI 50 represents severe hepatic impairment as measured in terminally ill CP (Child-Pugh) C cases with clinically advanced liver disease. Subjects with intermediate severity of liver disease have intermediate DSI scores.
- **STAT.** STAT is defined as the 60 minute d4-CA concentration from the SHUNT test, normalized to an ideal body weight of 75 kg. STAT was found in previous studies to correlate closely with DSI ( $r^2 = 0.88$ ). Utilizing this single blood sample will also be evaluated as a simplified testing approach.

For the purpose of the proposed analyses, DSI is considered the primary output variable from the HepQuant SHUNT test. However, in exploratory analyses we will determine the performance of the other test parameters – Systemic HFR, Portal HFR, SHUNT, and STAT.

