	We will also evaluate whether the HepQuant SHUNT test and DSI identify a treatment effect in the combined NASH F3 + NASH F4 cohorts, after unblinding of treatment assignments and completion of the primary analysis for Gilead's clinical trials. Treatment effect, as measured by DSI and $\Delta$ DSI, will be defined from the differences in DSI between treatment and placebo arms; and, compared to the treatment effect defined by changes in histology, standard laboratory tests, clinical models and by clinical outcomes.	
Secondary Objectives:	To determine the ability of baseline DSI, performed prior to treatment, to assess the severity of liver disease by: 1. correlation with other baseline tests of liver disease severity; and, 2. prediction of risk for future clinical outcome.	
Study Design:	Open Label HepQuant SHUNT Testing in All Subjects	
	STELLAR 3:	Baseline and Weeks 24, 48, and 240
	STELLAR 4:	Baseline and Weeks 24, 48, and 240
	GS-US-454-4378 (NASH F3 / F4):	Baseline and Weeks 24 and 48
Subjects, N:	Up to a total of 100 for all trials	
Clinical Sites, N:	Up to 15	
Target Populations:	NASH F3:	NASH Clinical Research Network (CRN) Fibrosis Stage 3
	NASH F4:	NASH CRN Fibrosis Stage 4 (compensated cirrhosis)
Compounds used in HepQuant SHUNT Test Kit:	[24-  C]cholic acid, 20 mg, intravenous injection	
	[2,2,4,4-  H(D)]cholic acid, 40 mg, oral solution	
Drug Treatment:	STELLAR 3:	Selonsertib vs Placebo
	STELLAR 4:	Selonsertib vs Placebo
	GS-US-454-4378 (NASH F3/F4):	Selonsertib, GS-0976, GS-9674 alone or in combination versus placebo.
Duration of Drug Treatment:	STELLAR 3:	240 weeks
	STELLAR 4:	240 weeks
	GS-US-454-4378 (NASH F3/F4):	48 weeks
Duration of Study and Drug Trial:	STELLAR 3:	252 weeks
	STELLAR 4:	252 weeks
	GS-US-454-4378 (NASH F3/F4):	52 weeks

Diagnostic and Eligibility Criteria:	Enrollment in the corresponding Gilead Trial, listed above
	Intravenous access for catheter placement
	Able to take orally administered solution
	No known allergy to any component of the HepQuant SHUNT test kit
Procedures and Frequency of the HepQuant SHUNT Testing:	
STELLAR 3:	Baseline and Weeks 24, 48, and 240
STELLAR 4:	Baseline and Weeks 24, 48, and 240
GS-US-454-4378 (NASH F3/F4):	Baseline and Weeks 24 and 48
Dose and Mode of Administration of Drug used in Drug Trial:	
STELLAR 3 and 4:	Selonsertib 6 or 18 mg orally daily

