### **5.3.4 Administration of the HepQuant SHUNT test**

Detailed instructions are provided in the Instructions for Use (Appendix B). The HepQuant SHUNT test is performed after an overnight fast or after at least 5 hours of fasting during the daytime. The morning dose of drug(s) is held until after completion of the HepQuant SHUNT test. The HepQuant SHUNT test requires venous access via a standard indwelling intravenous catheter, preferably placed in an antecubital vein. An oral solution of 4D-CA and an injectable solution of 13C-CA mixed with 25% human serum albumin are administered simultaneously over approximately 1 minute. If a problem is encountered with administering compounds simultaneously, the test is to be re-scheduled. If a rescheduled visit falls outside of the Gilead protocol-defined windows, sites should contact their study monitor for further instruction.

Blood samples are obtained at baseline and at  $5\pm 1$ ,  $20\pm 2$ ,  $45\pm 5$ ,  $60\pm 5$ , and  $90\pm 5$  minutes after cholate administration. The serum is separated and sent to the HepQuant laboratory for quantification of concentrations of endogenous cholate, 4D-CA and 13C-CA. Clearances are calculated from AUCs and dose and DSI and SHUNT are derived from the clearances.

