### **6.3.3 Formulations**

Cholates are purchased in powder form and both powders are dissolved in sodium bicarbonate solution (USP grade) to achieve concentrations of 4 mg/mL and passed through 0.22 micron filters. The absolute concentrations of 4D-cholate in the 4D-cholate solution and the 13C-cholate in the 13C-cholate solution will be defined by LCMS methods – concentrations typically range from 3.5 to 4.2 mg/mL.

d4-CA aliquots of 10 mL (~40 mg) will be transferred to sterile glass vials and stored at ambient temperature. For 13C-CA aliquots of 5.5 mL (~22 mg) will be transferred to sterile glass vials and stored at ambient temperature. Sterility and absence of pyrogens will be confirmed prior to use.

A central pharmacy will formulate the test compounds, perform the sterile filtering, and prepare the sterile aliquots. Once concentration and sterility are confirmed the cholate solutions are transferred to a kit maker for assemblage of the HepQuant SHUNT Liver Diagnostic Kit.

NOTE: The vial containing the oral dose of 4D-CA contains the exact amount of 10 mL of 4D-CA (~40 mg). But, in contrast, the vial containing the intravenous dose of 13C-CA contains approximately 5.5 mL of 13C-CA (~22 mg) – an excess of 0.5 mL (2 mg) to allow for aspiration of exactly 5 mL into a syringe. Accurate testing requires administration of the entire 10 mL of 4D-CA (~40 mg) oral solution; and, exactly 5 mL of 13C-CA (~20 mg) intravenously.

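### STAT, an exploratory output, has no dose term although the oral amount given can range from 35 to 42 mg; scaling it by the assayed dose would remove avoidable noise

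*Combined protocol and SAP*

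**What the plan says.** Section 3.1.3 of the combined protocol and SAP lists five test outputs. For STAT it says: "STAT is defined as the 60 minute d4-CA concentration from the SHUNT test, normalized to an ideal body weight of 75 kg". Body weight is the only adjustment named. In the same list the oral clearance behind Portal HFR "is defined as the dose/AUC for 4D-cholate", and Systemic HFR is built the same way from the intravenous tracer. Section 5.3.4 adds: "Clearances are calculated from AUCs and dose and DSI and SHUNT are derived from the clearances". Four of the five outputs therefore carry a dose term, directly or through the clearances, and STAT does not.

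Section 6.3.3 describes the solutions. The powders are dissolved "to achieve concentrations of 4 mg/mL and passed through 0.22 micron filters". The actual concentrations are then assayed; for the intravenous solution the text reads "the 13C-cholate in the 13C-cholate solution will be defined by LCMS methods", and the same sentence covers the oral one. It goes on to say that "concentrations typically range from 3.5 to 4.2 mg/mL". The oral volume is fixed: "Accurate testing requires administration of the entire 10 mL of 4D-CA (~40 mg) oral solution". The synopsis gives the oral compound as "cholic acid, 40 mg, oral solution".

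Section 3.1.3 makes DSI the primary output and places STAT among the exploratory parameters. It cites a previous r2 of 0.88 between STAT and DSI, and says the single sample will be evaluated as a simpler form of the test.

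**The concern.** A serum concentration at a fixed time depends on how much tracer was swallowed as well as on how fast the liver clears it. Dividing by dose, or fixing the dose, removes the first influence. STAT as defined does neither, because the volume is fixed while the concentration of the solution varies.

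Testing is serial: baseline and Weeks 24 and 48 in all three parent trials, with Week 240 added in the two STELLAR trials (Section 5.3.2). If a subject's kits come from preparations of different strength, part of the change in STAT between visits reflects the kit and not the liver. If the HFRs use the assayed dose, DSI is free of this component and STAT is not, so their agreement is lowered for a reason unrelated to whether one sample can stand in for six. What is at stake is the precision of an exploratory evaluation, and the error is removable with data the sponsor already plans to have.

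**Working it through.** **Inputs**
- Target concentration 4 mg/mL; typical assayed range 3.5 to 4.2 mg/mL; oral volume 10 mL (all Section 6.3.3).
- Nominal oral dose 40 mg (synopsis; written as approximately 40 mg in Section 6.3.3).
- STAT: 60-minute oral-tracer concentration, weight-normalized only (Section 3.1.3).

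**Step 1. Reproduce the plan's figure.** Dose = concentration x volume. 4 mg/mL x 10 mL = 40 mg, which matches. The same arithmetic gives the intravenous figures: 4 x 5.5 = 22 mg in the vial and 4 x 5 = 20 mg given.

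**Step 2. Range of the oral amount.** 3.5 x 10 = 35 mg; 4.2 x 10 = 42 mg.

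**Step 3. Effect on STAT.** Assume the 60-minute concentration is proportional to dose. The documents do not state this for a single time point, but treating dose over AUC as a clearance rests on the same linearity. STAT relative to its value at 40 mg is then dose / 40:
- at 35 mg: 35/40 = 0.875, or -12.5%
- at 42 mg: 42/40 = 1.05, or +5.0%
- weakest to strongest kit: 42/35 = 1.20, or +20.0%; in reverse 35/42 = 0.833, or -16.7%

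**Step 4. Typical size.** Assume, for scale only, that concentrations are spread evenly over the stated range. The dose then has mean (35 + 42)/2 = 38.5 mg and SD (42 - 35)/√12 = 2.02 mg:
- CV added to one test: 2.02/38.5 = 5.2%
- SD of a change between two independently drawn kits: √2 x 5.2% = 7.4% of the mean

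**Step 5. Effect of the correction.** Multiplying by 40/dose gives 0.875 x 40/35 = 1.00 and 1.05 x 40/42 = 1.00. Under the proportionality assumption the dose component disappears at every strength.

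**The case against.** The strongest reply is that this is small. STAT appears in no objective (Sections 2.1 and 2.2), not in the synopsis statistical methods, and nowhere in Section 8. It has no threshold, hypothesis or decision rule. That stands, and it limits the point to an improvement in an exploratory output.

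Second, the 20% is a contrast of extremes. Section 6.3.3 speaks of a typical range, does not use the word lot, and does not say how many batches this study needs or whether one subject's kits will differ between visits. With at most 100 subjects there may be few batches. That also stands: variation between visits within a subject is an inference, although a natural one where a central pharmacy prepares and assays the solutions. The Week 240 visit adds little, since Section 8.2.3 reports only 9 STELLAR subjects.

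Third, the earlier r2 of 0.88 may already include such variation if STAT was uncorrected then. That is possible, so no new loss against that figure can be claimed.

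Fourth, the Instructions for Use and the Investigator Brochure (Appendices B and F) are not in the text available here and might describe a correction. If so, Section 3.1.3 only needs to say it.

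A reader might go further and infer that the HFRs, SHUNT and DSI carry the same error because the calculation sections say only dose and the synopsis prints round figures. The documents do not support this. Those outputs have a dose term, Section 6.3.3 says the absolute concentrations are assayed and marks the doses as approximate, and nothing says nominal doses enter the calculation. A reader might also infer a biased treatment comparison. The parent trials are randomized and double-blind, and nothing links kit strength to arm, so the expected effect is mainly noise.

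**Conclusion.** The point holds for STAT alone. As defined in Section 3.1.3, STAT has no dose term while the oral amount can be 35 to 42 mg. It can therefore sit 12.5% below to 5% above its value at 40 mg, with 20% as the outer limit between two kits over the stated range. Under an even spread the added CV is about 5% per test, and the added SD is about 7% for a change between independent kits.

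These figures rest on three assumptions: that the 60-minute concentration is proportional to dose, that this study's kits cover the typical range, and, for the last two figures, that concentrations are evenly spread and kits are drawn independently. With fewer batches, or the same batch at each of a subject's visits, the effect on serial change is smaller or absent. The loss of agreement with DSI applies if the HFRs use the assayed dose. The primary DSI analysis is not shown to be affected.

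**What to change.** In Section 3.1.3, define STAT as the 60-minute d4-CA concentration x (40 mg / assayed oral dose), then normalized to 75 kg, where assayed oral dose = 10 mL x the LCMS-measured concentration of that kit's solution. Record the kit's measured concentration or batch with each test. As a clarification only, one sentence in Sections 3.1.3 and 5.3.4 could state that dose in both clearances means administered volume x LCMS concentration.

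This is a scaling in the analysis and leaves the administered dose unchanged. It costs one line of formula and one data field; the concentrations are already to be assayed, so no new sample or assay is needed. The real cost is comparability: earlier uncorrected STAT values, including the r2 of 0.88 if it was based on them, must be recomputed before they are set beside corrected ones.

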### 3.1.4 The HepQuant SHUNT Liver Diagnostic Kit

The test compounds,  $^{13}C$ -CA and d4-CA, and 25% human serum albumin are included in a HepQuant SHUNT Liver Diagnostic test kit with appropriate Instructions for Use. In brief, the contents of the kit include:

- Sealed vial of sterile solution of d4-CA (40 mg in 10 mL sodium bicarbonate) for oral use

- Sealed vial of sterile solution of  $^{13}\text{C}$ -CA (22 mg in 5.5 mL sodium bicarbonate) for intravenous use
- Sealed vial of 20 mL of 25% human serum albumin for intravenous use – 5 mL is added to 5 mL of the  $^{13}\text{C}$ -CA solution prior to intravenous injection
- 6 blood collection tubes (blood is allowed to clot and serum separated by centrifugation)
- 6 transfer tubes (for transport of serum to HepQuant designated lab)
- Labels
- Instructions for Use
- Mailer

### **3.1.5 Unmet Need**

The HepQuant SHUNT test fulfills an unmet medical need by providing a minimally-invasive test of global liver function and physiology. With progression, chronic liver disease (CLD) impairs hepatocyte function and the portal circulation - abnormalities which manifest as portal hypertension and portal-systemic shunting. HepQuant SHUNT measures the changes occurring in both the liver's function and the portal circulation.

In recognition of the limitations of standard lab tests, liver biopsy, and HVPG, the trans-NIH Action Plan for Liver Disease Research and the RFA for New Technologies for Liver Disease have clearly stated the need for “non-invasive means of assessing the liver” that would “obviate the need for liver biopsy in diagnosis, staging and grading of liver diseases” and that would “accurately reflect the stage of liver disease and can detect mild to moderate degrees of fibrosis before the onset of cirrhosis”. The minimally-invasive HepQuant SHUNT test fulfills most, if not all, of these criteria.

### **3.1.6 Measuring Hepatocyte Function**

For decades, investigators have used tests of hepatic metabolism to quantify hepatic function – most are insensitive, lack sufficient reproducibility, and require complex detection systems or analytical methods. However, none can measure the portal circulation or portal-systemic shunting – the latter being a key determinant of clinical complications of liver disease (varices, ascites and encephalopathy). The  $^{13}\text{C}$ -methacetin breath test is currently undergoing evaluation in trials; but it suffers from the same issues as other metabolic tests because it requires purchase of expensive bedside

equipment, and is influenced by gender, age, and use of many prescribed and OTC drugs or medications [22-25].

In head-to-head comparisons, the HepQuant SHUNT test performed favorably in comparison to a battery of metabolic tests in prediction of clinical outcomes. The metabolic substrates used in the metabolic tests as comparators were caffeine, antipyrine, lidocaine-MEGX, galactose, 13C-methionine, and 14C-erythromycin [7,8].

Key differences in the HepQuant SHUNT test, compared to metabolic tests, may explain its superior performance:

- HepQuant SHUNT is a dual clearance method tagging both systemic and portal inflow to the liver, i.e., it is a global clearance test.
- HepQuant SHUNT uses cholate, a compound with multiple hepatic transporters and relatively high first-pass hepatic extraction.
- Because multiple transporters are involved, a single nucleotide polymorphism in one transporter is not likely to influence overall cholate uptake.
- Cholate uptake is not dependent upon hepatocyte metabolism - drugs, medications, or other factors affecting cytochrome P450 metabolism.
- By comparing portal to systemic clearance of cholate, HepQuant SHUNT quantifies portal-systemic shunting, a key variable associated with and reflecting the meaningful clinical outcomes of varices, ascites, and encephalopathy.

### **3.1.7 Measuring the Portal Circulation**

Hepatic inflammation and fibrosis within the sinusoid and space of Disse increase the resistance to sinusoidal perfusion. The increase in hepatic resistance to portal inflow raises portal pressure - as CLD progresses, fibrosis accumulates, further raising hepatic resistance and leading to portal hypertension. The splanchnic bed adapts to the rise in portal pressure by vasodilatation and formation of portal-systemic collaterals leading to portal-systemic shunting [26].

Underlying portal hypertension (PH) is a risk factor for poor outcome in chronic liver disease (CLD). PH can be measured directly by percutaneous puncture of the liver to access the portal vein or by threading a catheter from the jugular vein into the portal vein to measure the hepatic venous pressure gradient (HVPG). Increased portal pressure or

HVPG correlates with risk of cirrhosis, varices, ascites, and decompensation. However, these tests are invasive, time consuming, risky, cumbersome, expensive, require specialized equipment and expertise, and are not embraced by subjects [27-29].

HepQuant SHUNT is a global function test capable of monitoring hepatocellular function, total hepatic perfusion, portal inflow to the liver, and portal-systemic shunting. Similar to HVPG, HepQuant SHUNT assesses the portal circulation. In contrast to HVPG, HepQuant SHUNT accomplishes this minimally-invasively with high patient tolerability and lower cost. These characteristics suggest that HepQuant SHUNT could be a minimally-invasive alternative to HVPG in monitoring the effects of liver disease on the portal circulation. In addition, these characteristics suggest that the HepQuant SHUNT test could be useful for detecting changes in response to treatments or interventions.

### **3.1.8 Measuring Disease Severity by the HepQuant SHUNT Test**

In our prior studies of chronic hepatitis C, DSI correlated with ISHAK and METAVIR stages of fibrosis and predicted likelihood of cirrhosis, varices, and risk for clinical outcome. DSI has performed similarly in subjects with chronic hepatitis C, non-alcoholic fatty liver disease (NAFLD), and primary sclerosing cholangitis [2-21].

### **3.1.9 Measuring Treatment Effect by the HepQuant SHUNT Test**

Serial changes in DSI have been assessed in subjects with chronic hepatitis C, during and after antiviral treatment, and in subjects with PSC. Two studies of HepQuant SHUNT for measuring impact of sustained viral response (SVR) are highlighted, GILEAD-sponsored SOLAR-1 and NIH-sponsored HALT-C. In SOLAR-1, subjects were treated with ledipasvir/sofosbuvir/ribavirin, and in HALT-C, subjects were treated with peginterferon/ribavirin. HepQuant SHUNT was performed at baseline and at weeks 4, 24, 36, and 48 in SOLAR-1; and, at baseline and after approximately 2 years in HALT-C. In the PSC study, subjects underwent HepQuant SHUNT tests at baseline and after 1 year.

In SOLAR-1, DSI improved significantly by week 4. The improvement was greatest in transplant recipients with necro-inflammation and non-cirrhotic stages of fibrosis ( $\Delta$ DSI  $-4.4 \pm 3.7$ ,  $p < 0.0001$ ) and in transplant recipients with cirrhosis ( $\Delta$ DSI  $-1.7 \pm 2.5$ ,  $p < 0.03$ ). DSI did not change in non-transplant subjects with end-stage decompensated disease

( $\Delta$ DSI  $0.2 \pm 2.8$ ,  $p = \text{NS}$ ). Standard laboratory tests, MELD score, and CTP score failed to detect the improvement in liver function at week 4 [20].

The results of SOLAR-1 suggest that the decrease in DSI by week 4 was likely due to improvement in the hepatic microcirculation. First, ALT declined in parallel with the clearance of HCV RNA indicating reduction in necro-inflammation. Second, platelet count increased in LT Fibrosis and LT Cirrhosis, most probably from a reduction in splenic sequestration as hepatic resistance declined and portal hypertension improved. Third, the increase in platelet count correlated with the decrease in DSI. Fourth, although improvement in hepatocyte uptake of cholate might also account for the increases in HFRs and decline in DSI, there was no improvement in blood tests of hepatocyte function, such as bilirubin, albumin and INR. These findings are consistent with the interpretation that early hepatic improvement measured by drop in DSI reflects improvement in the hepatic microcirculation.

Because in CLD, necro-inflammation is a hallmark of the injury, baseline DSI will define the severity of the hepatic impairment at start of treatment. With successful treatment by selonsertib, necro-inflammation should be reversed and be manifested as improved hepatic perfusion and hepatocyte uptake – events that should be detected by drop in DSI from the baseline test. If selonsertib has a very rapid onset of action, we could possibly detect improvement at the earliest time point after initiating treatment.

The serial studies in HALT-C and PSC may not be as relevant to detection of early treatment effect since the follow-up DSI in these studies was either 1 year (PSC) or 2 years (HALT-C) after baseline testing. Nonetheless, the results in HALT-C demonstrated significant improvement in DSI after SVR and worsening of DSI in both untreated subjects and treated subjects who remained infected [4]. The study of DSI in PSC subjects identified 3 progressor groups of PSC subjects, slow, moderate, or rapid, based on DSI relative to age and the change in DSI over one year. The serial changes in DSI over one year confirmed slower progression in the slow progressor group compared to a more rapid rate of progression in the moderate to rapid progressor groups [18].

